4.6.1.1 MGI Repeatability

The first and repeat values of the MGI for each tooth site will be combined and cross-tabulated for the MGI Repeatability population (Table 14.2.8.1). Only subjects with both first and repeat MGI assessments available for a given tooth site at the same visit will be presented and analyzed.

4.6.1.2 TPI Repeatability

The first and repeat values of the TPI for each tooth site will be combined and cross-tabulated for the TPI Repeatability population (Table 14.2.9.1). Only subjects with both first and repeat TPI assessments available for a given tooth site at the same visit will be presented and analyzed.

5 Changes to the Protocol Defined Statistical Analysis Plan

Changes from the originally planned statistical analysis specified in the protocol are outlined in [Table 5-1](#) below.

Table 5-1 Changes to the Protocol Defined Statistical Analysis Plan

Protocol	Statistical Analysis Plan	
Statistical Analysis Section	Statistical Analysis Plan	Rationale for Changes
Section 6.3.1 of the Protocol states that 'The results of the examination will be recorded in the eCRF as either 'normal' or 'abnormal'.	Section 4.5.2.1 of the SAP has revised the Protocol text to state that 'Any abnormal findings from the OST examination will be recorded in the eCRF with details of the abnormalities.'	This study uses a redesigned standard eCRF, where only abnormal results will be captured in the eCRF for OST examination.
Section 6.3.2 of the Protocol states that 'Conditions will be listed as 'absent' or 'present'; those noted as 'present' will be described in the eCRF'.	Section 4.5.2.2 of the SAP has revised the Protocol text to state that 'Any conditions noted as 'Present' from the OHT examination will be described in the eCRF along with the details of the 'Present' condition.'	This study uses a redesigned standard eCRF, where only 'Present' conditions will be captured in the eCRF for OHT examination.

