**CCI**

Abbreviated Clinical Protocol Template v1.0

Page 13 of 53

removed. Any residual plaque and/or calculus will be removed to bring the subject to zero plaque (TPI = 0) before entering the treatment period.

Subjects will be then stratified based on gender and baseline mean whole mouth MGI score (Low:  $\leq 2.00$ /High  $> 2.00$ ), to ensure a balance of gingivitis across both treatment groups and will be then randomized to study products. Gender is a known modifier of the initiation and outcome of conditions related to gingival health ([Alam, Mishra et al. 2012](#)). Stratifying by MGI will facilitate evaluation of BI and MGI in low and high MGI subgroups.

The MGI and the BI are established clinical measures of gingival inflammation and gingival bleeding, respectively (i.e. gingival health); the TPI is an established clinical measure of supra-gingival plaque accumulation. To avoid inter-examiner variability, a single examiner will be responsible for the conduct of each of the clinical indices (MGI, BI, TPI).

Randomized subjects will then receive their assigned study product, a toothbrush, rinsing cups and instructions on product usage. Subjects will be instructed to brush twice daily (morning and evening) with their allocated study product, in their usual manner, for 1-timed minute for the next 4 weeks. They will complete the first brushing at the study site, under supervision.

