## CCI

After using the study products for 4 weeks, subjects will return to the study site (Visit 3) with overnight plaque (subjects will be instructed to abstain from overnight toothbrushing for 12 hours [+3 hours; -2 hours] immediately before each assessment visit), at approximately the same time of day as the Baseline visit. Changes in health/concomitant medications will be recorded and compliance check will be performed by visual inspection of study products by study staff to ensure adequate brushing. Subjects will then have a full OST examination followed by a **CCI** [REDACTED], MGI, BI and TPI assessments.

Subjects will be offered a standardised snack and then will be asked to brush their teeth on site, under supervision, with the assigned toothpaste. **CCI** [REDACTED]. Subjects will also have a full final OST/OHT examination.

At the end of V3 (Week 4), study closeout procedures (return of study product etc.) will take place and the subject may undergo an additional prophylaxis if it is deemed necessary by the examiner. Adverse events (AEs) will be recorded from informed consent and at the end of each study visit.

Haleon

Clinical Protocol

Protocol Number: 300178

To assess examiner reproducibility across the treatment period, repeat MGI and TPI assessments will be performed on selected subjects at Visits 2-3. (Replicate BI examinations cannot be performed due to the inherent invasiveness of this measure). At least 3 subjects will be selected for repeatability examinations for each of the 2 clinical measures over the duration of each of visits 2 and 3. This will give a total of at least 6 subjects with repeatability examinations for each of the MGI and TPI assessments across the entire study. Repeatability examinations should be separated by a minimum of 10 minutes and, where possible, separated by another subject. MGI and TPI repeat assessments should be performed on different subjects.

All assessments will be carried out on the facial and lingual/palatal surfaces of each incisor, canine, pre-molar and molar, excluding third molars. To control inter-examiner variability, the same examiner will be used throughout the study for each clinical index.

Subjects will not be able to eat or drink, except for small sips of water used to alleviate thirst or to aid with medication, following supervised brushing at V2 and V3 **CCI**

**CCI** .

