4.1.3 Analysis Populations

Five analysis populations are defined.

Population	Definition / Criteria	Analyses Evaluated
Safety	Comprise of all randomized subjects who receive at least one dose of investigational product. Summaries and analyses of this population will be based on the investigational product the subject received.	
DemographicsSafety
Modified Intent-To-Treat (mITT)	Comprise of all randomized subjects who receive at least one dose of investigational product and complete at least one-post Baseline BI assessment. This population will be based on the investigational product the subject was randomized to. All subjects who receive a randomization number will be considered randomized.	
DemographicsComplianceEfficacy
Per-Protocol (PP)	Comprise of all subjects in the mITT population who have at least one non-missing BI assessment considered to be unaffected by protocol deviations. Protocol deviations that may exclude subjects from the PP population are defined in Section 4.1.2 (Protocol Deviations).	
Efficacy
MGI Repeatability	Comprise of all subjects who have at least one repeat MGI clinical assessment at any visit.	
Repeatability for MGI
TPI Repeatability	Comprise of all subjects who have at least one repeat TPI clinical assessment at any visit.	
Repeatability for TPI

NOTE:

Please refer to [Appendix 1](#): List of Data Displays, which details the population to be used for each display being generated.

The number of subjects included in each of the analysis populations will be presented (Table 14.1.1). Subjects excluded from any of the analysis populations will be listed in Listing 16.2.3.1, with the reason for exclusion.

The primary population for assessment of efficacy will be the mITT population. A PP analysis will be performed on the primary endpoint only if more than 10% of mITT subjects are excluded from the PP population. A decision on whether a PP analysis will be performed will be made prior to study unblinding (release of the randomization codes).

Any repeat clinical data collected for the repeatability assessment will only be used to assess repeatability. The main assessment of efficacy will be based on the initial assessment.

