4.6 Analysis of Other Variables

4.6.1 Repeatability of the Examiner

Repeat MGI and TPI assessments will be performed by the clinical examiners at Visits 2 and 3. At least 3 subjects will be selected for repeat assessments over the duration of each of visits 2 and 3. Thus a total of at least 6 subjects repeat assessments for each endpoint will be collected during this study. 'Repeat' subjects will be selected at random from those in attendance on any given assessment day. Different subjects should be used for repeat MGI and TPI assessments.

There should be a delay of at least 10 minutes between the original and the repeat assessment for a given subject; ideally, repeat assessments should be separated by another subject. No other clinical procedure should be carried out on the selected subject between repeat assessments.

Scores from the first assessment must not be visible to the examiner/scribe when the repeat assessment is carried out.

The repeat MGI and TPI assessments will be compared to the respective original assessments (excluding any tooth surfaces assessed as missing or not qualified). The repeat assessments will not be used in any efficacy analysis.

The first and second assessments of each index will be analyzed with a Fleiss-Cohen weighted kappa coefficient (κ), along with the 95% CI, to assess the intra-examiner reliability. Reliability will be deemed:

- Excellent if $\kappa > 0.75$

- Fair to good if $0.4 \leq \kappa \leq 0.75$
- Poor if $\kappa < 0.4$

This analysis will be conducted on each respective index repeatability population (MGI population and TPI population).

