14.2 Efficacy Data Summary Tables and Figures						
	Table	14.2.1	Summary of Brushing Compliance	mlITT Population	14.2.1	
	Table	14.2.2.1.1	Summary of Bleeding Index (BI)	mlITT Population	14.2.2.1.1	Yes
	Table	14.2.2.1.2	Summary of Bleeding Index (BI)	PP Population	14.2.2.1.1	
	Figure	14.2.2.1.3	Bleeding Index (BI) (\pm SE) Plot Over Time by Study Product	mlITT Population	14.2.2.1.3	
	Figure	14.2.2.1.4	Bleeding Index (BI) (\pm SE) Plot Over Time by Study Product	PP Population	14.2.2.1.3	
	Table	14.2.2.2.1	Statistical Analysis of Bleeding Index (BI)	mlITT Population	14.2.2.2.1	Yes
	Table	14.2.2.2.2	Statistical Analysis of Bleeding Index (BI)	PP Population	14.2.2.2.1	
	Table	14.2.3.1.1	Summary of Number of Bleeding Sites	mlITT population	14.2.2.1.1	

CSR Section	TLF	Number	Title	Population	Template	Topline
	Figure	14.2.3.1.2	Number of Bleeding Sites (\pm SE) Plot over Time by Study Product	miITT Population	14.2.2.1.3	
	Table	14.2.3.2.1	Statistical Analysis of Number of Bleeding Sites	miITT Population	14.2.2.2.1	
	Table	14.2.4.1.1	Summary of Modified Gingival Index (MGI)	miITT Population	14.2.2.1.1	Yes
	Figure	14.2.4.1.2	Modified Gingival Index (MGI) (\pm SE) Plot Over Time by Study Product	miITT Population	14.2.2.1.3	
	Table	14.2.4.2.1	Statistical Analysis of Modified Gingival Index (MGI)	miITT Population	14.2.2.2.1	Yes
	Table	14.2.5.1.1	Summary of Overall Turesky Plaque Index (TPI)	miITT Population	14.2.2.1.1	
	Figure	14.2.5.1.2	Overall Turesky Plaque Index (MGI) (\pm SE) Plot Over Time by Study Product	miITT Population	14.2.2.1.3	
	Table	14.2.5.2.1	Statistical Analysis of Overall Turesky Plaque Index (TPI)	miITT Population	14.2.2.2.1	Yes
	Table	14.2.6.1.1	Summary of Interproximal Turesky Plaque Index (TPI)	miITT Population	14.2.2.1.1	
	Figure	14.2.6.1.2	Interproximal Turesky Plaque Index (TPI) (\pm SE) Plot Over Time by Study Product	miITT Population	14.2.2.1.3	
	Table	14.2.6.2.1	Statistical Analysis of Interproximal Turesky Plaque Index (TPI)	miITT Population	14.2.2.2.1	
CCI						

CSR Section	TLF	Number	Title	Population	Template	Topline
			CCI			
	Table	14.2.8.1	Intra-Examiner Repeatability Analysis of Modified Gingival Index (MGI)	MGI Repeatability	14.2.8.1	
	Table	14.2.9.1	Intra-Examiner Repeatability Analysis of Turesky Plaque Index (TPI)	TPI Repeatability	14.2.9.1	

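### One pooled kappa per index cannot show whether examiner repeatability held from Baseline to Week 4, and it may sit above the within-visit values

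*SAP*

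**What the plan says.** Protocol Section 3 gives the purpose: "To assess examiner reproducibility across the treatment period, repeat MGI and TPI assessments will be performed on selected subjects at Visits 2-3". At least 3 subjects per index are repeated at each of Visits 2 and 3, so at least 6 per index over the study.

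SAP 4.6.1 sets the statistic: the two readings "will be analyzed with a Fleiss-Cohen weighted kappa coefficient", with a 95% CI and three labels (excellent above 0.75, fair to good from 0.4 to 0.75, poor below 0.4).

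Three places point to one pooled result per index:

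- SAP 4.6.1.2, for TPI: "The first and repeat values of the TPI for each tooth site will be combined and cross-tabulated for the TPI Repeatability population". SAP 4.6.1.1, for MGI: "The first and repeat values of the MGI for each tooth site will be combined and cross-tabulated for the MGI Repeatability population".
- SAP 4.1.3 defines the TPI repeatability population without regard to visit: "Comprise of all subjects who have at least one repeat TPI clinical assessment at any visit". The MGI population is defined in the same way.
- SAP Appendix 1 lists one repeatability table per index (14.2.8.1 and 14.2.9.1) and no by-visit version.

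Visit appears only in the rule "Only subjects with both first and repeat TPI assessments available for a given tooth site at the same visit will be presented and analyzed". That rule says which two readings form a pair. It does not split the table.

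**The concern.** The two visits are scored in different conditions. At Baseline, subjects have been selected for mean MGI 1.75 to 2.30 and mean TPI of at least 1.5. After those scores are taken, Protocol Section 3 says: "Any residual plaque and/or calculus will be removed to bring the subject to zero plaque (TPI = 0) before entering the treatment period". Week 4 scores follow that cleaning and four weeks of product use. A lower level at Week 4 is a reasonable expectation, although its size is not stated.

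Two things can then go wrong with a single kappa:

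1. A quadratic-weighted kappa behaves like an intraclass correlation. A gap in level between visits adds to the variance that it treats as real, so the pooled value can exceed what the examiner achieves at either visit.
2. If repeatability is lower at one visit, pooling averages it with the better visit. The label can then be one that the weaker visit would not earn.

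At stake is the stated aim. Repeats are collected at both visits to describe reproducibility over the treatment period, and one merged figure cannot show a change over that period.

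**Working it through.** **Plan's own figure.** 3 subjects × 2 visits = 6 per index, as stated. The plan gives no expected kappa, site-score SD or fall between visits, so everything below rests on assumed values.

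**Formula for a level gap.** Let both visits have kappa k and the same total SD, with equal numbers of pairs and means d total-SD units apart. Disagreement within pairs is unchanged, while total variance grows by the factor 1 + d²/4. Hence

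pooled κ = 1 − (1 − k)/(1 + d²/4) = (k + d²/4)/(1 + d²/4).

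**Numbers for TPI.** Assumed: latent mean 2.8, site SD 0.9, reading-error SD 0.5, readings rounded to 0–5. Simulation gives within-visit κ = 0.707 and an observed SD of about 1.06.

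- Fall 0.5: d = 0.5/1.06 = 0.472 and d²/4 = 0.056, so κ = (0.707 + 0.056)/1.056 = 0.72.
- Fall 1.0: d = 1.0/1.06 = 0.943 and d²/4 = 0.222, so κ = (0.707 + 0.222)/1.222 = 0.76.

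Direct simulation (400,000 pairs per visit), with examiner error the same at both visits:

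| Index | Within-visit κ | Fall | Pooled κ |
|---|---|---|---|
| TPI | 0.71 | 0.5 | 0.72 |
| TPI | 0.71 | 0.75 | 0.74 |
| TPI | 0.71 | 1.0 | 0.76 |
| TPI | 0.71 | 1.5 | 0.80 |
| MGI | 0.64 | 0.3 | 0.65 |
| MGI | 0.64 | 0.5 | 0.67 |
| MGI | 0.64 | 0.8 | 0.72 |

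The MGI rows assume mean 2.0, site SD 0.6 and error SD 0.35. A second TPI model (subject SD 0.3, site SD 0.75, error SD 0.42; 3 subjects per visit, 144 sites each) takes a within-visit 0.70 to 0.73, 0.75 and 0.77 for falls of 0.5, 0.75 and 1.0. Across the two models the excess is 0.015 to 0.03 for a fall of 0.5 and 0.05 to 0.07 for a fall of 1.0.

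**Fall needed to cross 0.75.** Solving the formula gives d = 2√((0.75 − k)/0.25): 0.9 SD from k = 0.70, 1.3 SD from 0.65 and 1.5 to 1.6 SD from 0.60.

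**Unequal repeatability, no fall.** With equal total variance, pooled κ = (k₂ + k₃)/2. If Baseline is 0.85, the pooled value exceeds 0.75 whenever Week 4 exceeds 2 × 0.75 − 0.85 = 0.65. Simulation, letting the error SD grow at Week 4:

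| TPI κ Baseline | TPI κ Week 4 | Pooled, fall 0 | Pooled, fall 1.0 |
|---|---|---|---|
| 0.85 | 0.71 (fair to good) | 0.77 (excellent) | 0.82 (excellent) |
| 0.85 | 0.58 (fair to good) | 0.69 (fair to good) | 0.75 (fair to good) |
| 0.85 | 0.34 (poor) | 0.50 (fair to good) | 0.57 (fair to good) |

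**Check on the remedy.** By-visit kappa also depends on spread. In the second TPI model, run with mean 2.8 and large samples, keep the error SD at 0.42 and reduce the site SD from 0.75 to 0.55. Kappa falls from 0.71 to 0.60. Exact agreement stays at 55% and the mean squared difference at 0.52. The fall in kappa is not examiner drift.

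**The case against.** **The pooled kappa has a legitimate target.** Kappa is specific to the score range sampled, and agreement over the whole range seen in the study is a meaningful quantity. This stands: pooling is not an error in itself, and the pooled value can stay. It does not answer whether agreement held over time.

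**The reading is likely, not certain.** SAP 4.6.1.1 and 4.6.1.2 do not say that it is visits that are combined, and the table shells are not in the documents. By-visit panels inside Tables 14.2.8.1 and 14.2.9.1 cannot be ruled out. If they are intended, one sentence in the SAP settles the matter.

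**The size is unknown.** Week 4 plaque is scored after 10 to 15 hours without brushing, and about half the subjects use the negative control, so a TPI fall of 1.0 cannot be taken as given. This stands. For falls of up to 0.5 TPI or 0.3 MGI the simulated excess is at most about 0.03.

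**Stronger readings that the documents do not support.** A reader might infer that the pooled kappa hides any loss of repeatability. It does not: 0.78 then 0.58, with a TPI fall of 0.75, pools to 0.71, the same label as Week 4 alone. A reader might also infer that only Week 4 repeatability matters because the endpoints are Week 4 scores. Baseline MGI and TPI set eligibility, Baseline MGI sets the strata, and the baseline values enter the models as covariates (Protocol 8.3.1 and 8.3.2; SAP 4.4.1.2 and 4.4.2). Both visits matter.

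**Conclusion.** The point holds as a minor improvement to a descriptive analysis. On the natural reading, one kappa per index merges two visits whose score levels may differ. The pooled value may then exceed the within-visit values, by about 0.02 for a TPI fall of 0.5 and about 0.06 for 1.0. These sizes come from assumed score models, and the excess is nil if the level does not change. The dilution of a weaker visit needs no fall: 0.85 and 0.71 pool to 0.77 and change the label. A large loss still lowers the pooled figure, so it is diluted, not erased.

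The documents do not show that the reported kappa will be inflated, nor that a reliability label will be wrong. They show that the planned output cannot tell. Repeat scores are excluded from every efficacy analysis, no stated decision depends on the label, and the primary endpoint, BI, has no repeat assessment. Efficacy inference and power are untouched.

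**What to change.** In SAP 4.6.1 and Tables 14.2.8.1 and 14.2.9.1, present the cross-tabulation, weighted kappa and 95% CI separately for Visit 2 and Visit 3, beside the pooled value. State that the reliability label does not rest on the pooled value alone. Add a raw agreement measure by visit, such as percent exact agreement or mean squared difference, so that a lower kappa caused by narrower spread is not read as examiner drift.

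A visit-stratified average kappa would remove the effect of the level gap but not the dilution, so it does not replace the by-visit display.

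The cost is a few lines of SAP text and a by-visit split in two tables, using data already planned. The downside is precision: each by-visit kappa may rest on as few as 3 subjects, with many sites clustered within each. The intervals should allow for that clustering and the labels should be read cautiously.

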Appendix 1: List of Data Displays

CSR Section	TLF	Number	Title	Population	Template	Topline
14.1 Demographic Data Summary Tables and Figures						
	Table	14.1.1	Subject Disposition	All Screened Subjects	14.1.1	Yes
	Table	14.1.2	Incidence of Important Protocol Deviations	All Randomized Subjects	14.1.2	
	Table	14.1.3.1	Demographic and Baseline Characteristics	Safety Population	14.1.3.1	
	Table	14.1.3.2	Demographic and Baseline Characteristics	mlITT Population	14.1.3.1	Yes
	Table	14.1.3.3	Demographic and Baseline Characteristics	PP Population	14.1.3.1	
14.2 Efficacy Data Summary Tables and Figures						
	Table	14.2.1	Summary of Brushing Compliance	mlITT Population	14.2.1	
	Table	14.2.2.1.1	Summary of Bleeding Index (BI)	mlITT Population	14.2.2.1.1	Yes
	Table	14.2.2.1.2	Summary of Bleeding Index (BI)	PP Population	14.2.2.1.1	
	Figure	14.2.2.1.3	Bleeding Index (BI) (\pm SE) Plot Over Time by Study Product	mlITT Population	14.2.2.1.3	
	Figure	14.2.2.1.4	Bleeding Index (BI) (\pm SE) Plot Over Time by Study Product	PP Population	14.2.2.1.3	
	Table	14.2.2.2.1	Statistical Analysis of Bleeding Index (BI)	mlITT Population	14.2.2.2.1	Yes
	Table	14.2.2.2.2	Statistical Analysis of Bleeding Index (BI)	PP Population	14.2.2.2.1	
	Table	14.2.3.1.1	Summary of Number of Bleeding Sites	mlITT population	14.2.2.1.1	

CSR Section	TLF	Number	Title	Population	Template	Topline
	Figure	14.2.3.1.2	Number of Bleeding Sites (\pm SE) Plot over Time by Study Product	miITT Population	14.2.2.1.3	
	Table	14.2.3.2.1	Statistical Analysis of Number of Bleeding Sites	miITT Population	14.2.2.2.1	
	Table	14.2.4.1.1	Summary of Modified Gingival Index (MGI)	miITT Population	14.2.2.1.1	Yes
	Figure	14.2.4.1.2	Modified Gingival Index (MGI) (\pm SE) Plot Over Time by Study Product	miITT Population	14.2.2.1.3	
	Table	14.2.4.2.1	Statistical Analysis of Modified Gingival Index (MGI)	miITT Population	14.2.2.2.1	Yes
	Table	14.2.5.1.1	Summary of Overall Turesky Plaque Index (TPI)	miITT Population	14.2.2.1.1	
	Figure	14.2.5.1.2	Overall Turesky Plaque Index (MGI) (\pm SE) Plot Over Time by Study Product	miITT Population	14.2.2.1.3	
	Table	14.2.5.2.1	Statistical Analysis of Overall Turesky Plaque Index (TPI)	miITT Population	14.2.2.2.1	Yes
	Table	14.2.6.1.1	Summary of Interproximal Turesky Plaque Index (TPI)	miITT Population	14.2.2.1.1	
	Figure	14.2.6.1.2	Interproximal Turesky Plaque Index (TPI) (\pm SE) Plot Over Time by Study Product	miITT Population	14.2.2.1.3	
	Table	14.2.6.2.1	Statistical Analysis of Interproximal Turesky Plaque Index (TPI)	miITT Population	14.2.2.2.1	
CCI						

CSR Section	TLF	Number	Title	Population	Template	Topline
			CCI			
	Table	14.2.8.1	Intra-Examiner Repeatability Analysis of Modified Gingival Index (MGI)	MGI Repeatability	14.2.8.1	
	Table	14.2.9.1	Intra-Examiner Repeatability Analysis of Turesky Plaque Index (TPI)	TPI Repeatability	14.2.9.1	
14.3 Safety Data Summary Tables and Figures						
14.3.1 Displays of Adverse Events						
	Table	14.3.1.1	Treatment Emergent Adverse Events Overall Summary	Safety Population	14.3.1.1	Yes
	Table	14.3.1.2	Treatment Emergent Adverse Events by System Organ Class and Preferred Term	Safety Population	14.3.1.2	
	Table	14.3.1.3	Treatment Emergent Adverse Events by Oral/Non-Oral and Preferred Term	Safety Population	14.3.1.3	
	Table	14.3.1.4	Treatment Related Treatment Emergent Adverse Events by System Organ Class and Preferred Term	Safety Population	14.3.1.2	

CSR Section	TLF	Number	Title	Population	Template	Topline
	Table	14.3.1.5	Treatment Related Serious Treatment Emergent Adverse Events by Oral/Non-Oral and Preferred Term	Safety Population	14.3.1.3	
